9.2 Handling of the Difference between the Scheduled and the Actual Sampling Times

The actual clock time for study drug administration and each collection time for the PK samples will be recorded. For all sampling times, the actual sampling times relative to study drug administration will be calculated as the difference between the actual clock time of sampling and the actual clock time of study drug administration. The actual post-dose sampling times relative to study drug administration expressed in hours and rounded off to three decimal digits will be used to calculate the PK parameters, except for pre-dose samples occurring prior to study drug administration, which will always be reported as zero (0.000), regardless of the time difference. Scheduled sampling times (presented as 3 numbers [i.e. 0.50, 0.75, 1.00 or 24.0]) will be presented in concentration tables and mean graphs, while actual sampling times will be presented in the individual graphs.

9.3 PK Sampling Schedule

Blood samples will be collected from each subject during this study for the determination of the PK of esomeprazole.

PK blood samples of esomeprazole will be drawn according to the following schedule:

This document is confidential.

Pre-dose (within 1 hour before study drug administration) and at 0.5-, 0.75-, 1-, 1.25-, 1.5-, 1.75-, 2-, 2.25-, 2.5-, 2.75-, 3-, 3.5-, 4-, 4.5-, 5-, 5.5-, 6-, 8-, 10-, 12-, 16-, and 24-hours following dosing in each treatment period. The time tolerance window for blood samples will be ± 1 minute for all samples collected before 8 hours post-dose and ± 3 minutes for subsequent samples.

Samples obtained outside the pre-defined time windows will not be captured as a protocol deviation, as long as the exact time of the sample collection is noted on the source document and data collection tool (e.g. CRF).

9.4 Plasma Pharmacokinetic Parameters

Plasma concentrations from esomeprazole will be used to calculate the following PK parameters by standard non-compartmental methods:

PK Parameter	Definition
Primary PK Parameters	
AUC _{0-t}	Area under the plasma concentration versus time curve from time zero to time t, where t is the time of the last measurable plasma concentration of esomeprazole, computed using the linear trapezoidal rule
C _{max}	The maximum observed post-dose concentration; obtained without interpolation
Secondary PK Parameters	
AUC _{0-inf}	Area under the plasma concentration versus time curve calculated from time zero to infinity. $AUC_{0-inf} = AUC_{0-t} + C(t)/\lambda_z$ where C(t) is the concentration at the last measurable sampling time point and λ_z is the terminal elimination rate constant
%AUC _{ex}	Percentage of AUC _{0-inf} obtained by extrapolation, calculated as $(1 - [AUC_{0-t} / AUC_{0-inf}]) \times 100$
t _{max}	Time of the maximum observed post-dose concentration
t _{1/2}	Elimination half-life computed as $t_{1/2} = \ln(2) / \lambda_z$
λ_z	Terminal elimination rate constant computed as the slope of the regression line of $\ln(C(t))$ on time. The regression should generally involve at least 3 consecutive measurable concentrations that decrease over time.

The adjusted coefficient of determination (R^2 adjusted) in general should be greater than 0.80. All the derived parameters (e.g., λ_z , t_{1/2}, AUC_{0-inf}) will be flagged accordingly for exclusion from summary statistics and statistical modeling as appropriate. The time point where ln-linear λ_z calculation begins (λ_z lower), the actual sampling time of the last quantifiable concentration used to estimate the λ_z (λ_z upper) as well as the R^2 adjusted for the ln-linear regression for the calculation of the elimination rate constant calculation will be reported.

This document is confidential.

9.5 Statistical Analyses

The following statistical analysis will be based on the PK Analysis Set.

Individual plasma concentrations will be summarized descriptively at each time point; the concentration vs. time profile will be graphed by formulation for individual subjects and for the arithmetic mean (\pm SD) on both original and logarithmic scales for the safety population. For ease of presentation, actual and scheduled sampling times will be used to present results for individual and mean figures respectively. Individual subject data will also be listed.

The PK parameters (AUC_{0-t} , and C_{max}) will be summarized for each treatment by descriptive statistics.

The PK parameters (AUC_{0-inf} , $\%AUC_{ex}$, λ_z , t_{max} , and $t_{1/2}$) will be summarized for each treatment using descriptive statistics same as for the primary PK parameters.

9.6 Assessment of Bioequivalence

[figure not shown]
The primary objective will be evaluated based on the following comparison:

Esomeprazole CG (Test) versus esomeprazole AZ (Reference), in terms of esomeprazole AUC_{0-t} and C_{max} .

A linear mixed effects model will be fitted to the log-transformed PK variables (AUC_{0-t} or C_{max}), as the dependent variable, and treatment, sequence, and period as fixed effects. Subject nested within sequence will be a random effect. Least squares estimates of treatment effects will be calculated and a 90% confidence interval (CI) for the treatment difference will be computed. The treatment difference and its CI will be exponentiated to obtain the ratio of the geometric means between the test and reference products (test/reference) and its CI.

Bioequivalence will be declared for AUC_{0-t} if the 90% 2-sided CI for the ratio lies completely within the range of 0.8-1.25 and for C_{max} if the point estimate for the ratio lies completely within the range of 0.8-1.25. No further adjustments for multiplicity of the co-primary endpoints are necessary as both endpoints must be met in order to achieve study success.

The SAS code for the analysis model will follow the format given below (The input variables (or datasets) are depicted in slanted red text and have been given generic names).

9.6.1 Group Effect Analysis

This study is planned to dose in more than 1 groups. The group effect will be added to the model

This document is confidential.

Version: Draft 1.0 11-Mar-2022

Controlled Document ID: CCI, Effective Date 29-Jul-2019

Filing requirements: TMF

[figure not shown]
as described in Section 9.6 based on the following criteria:

- If the two groups are dosed more than 4 weeks (28 days) apart the group
 - a. All subjects have been recruited from the same enrollment pool (The enrollment pool will be considered the same if all subjects from the second group are not screened after dosing of the first group).
 - b. All subjects have similar demographics.
 - c. The clinical study takes place at one site.
 - d. All enrolled subjects are randomly assigned treatment groups at study outset.

Because this is a single center study with well-defined enrollment criteria for subject in respects to demographics, points B and C are met by definition of the study. A single randomization was also provided for all subjects before any dosing for the study was performed, including 49 subjects. If additional randomization is required after dosing 2 groups due to a larger than expected drop out rate, this point will not be met and the effect of group would be included in the statistical model. Otherwise, the primary criteria for the decision of adding the group effect will be based on the time between the two groups and the screening period of all subjects.

If the group effect is determined to be necessary, the following fixed terms will be included in the model: group, sequence, group by sequence, period within group, and treatment. The ratio and 90% CI will be calculated for AUC_{0-t} and C_{max} as applicable.

The SAS code for the analysis model will follow the format given below (The input variables (or datasets) are depicted in slanted red text and have been given generic names).

10. Safety

All safety analyses will be based on the Safety Population. Safety will be assessed on the basis of adverse event (AE), clinical laboratory data, vital signs, and physical examination.

10.1 Adverse Events

The assessment of safety will be based on the frequency and severity of AEs that are collected immediately after a subject provides consent to participate in the study by the completion (signature) of the ICF and until 5 days following last administration of the study product.

Treatment-emergent AEs (TEAEs) and non-TEAEs will be listed by subject and treatment.

This document is confidential.

Version: Draft 1.0 11-Mar-2022

Controlled Document ID: CCI, Effective Date 29-Jul-2019

Filing requirements: TMF

TEAEs will be defined as any AEs that first occurs on or after the date and time of first drug administration. Any AE that first occurs pre-dose but worsens in severity after the first study drug administration will also be considered a TEAE. Non-TEAEs are those that occur prior to the first administration of the study medication and resolved prior to study drug administration or that first occur prior to the first study drug administration but do not worsen in severity after study drug administration. AEs will be captured during the study until study exit. All AEs (serious and non-serious) will be followed until resolution, until the condition stabilizes, until the event is otherwise explained, or until the subject is lost to follow-up. .

Adverse events will be coded using the MedDRA® dictionary Version 24.1. The incidence of AEs will be tabulated (for each treatment) after grouping by preferred term within System Organ Class (SOC). AEs will be summarized as the number and percentage of subjects having any AE, an AE by SOC, and AE by preferred term within SOC. Treatment-emergent AEs will also be summarized by SOC, PT, and maximum severity. The subset of AEs suspected of a relationship to study drug administration (related: probable, possible, remote, or not related: unrelated) will be summarized similarly. All AEs will also be tabulated by severity (mild, moderate, or severe). AEs will be assigned to the treatment administered immediately prior to the onset. Adverse events due to COVID-19, if any, will be listed and tabulated separately.

The relationship of TEAEs will be classified according to the study protocol as unrelated or related (remote, possible, or probable) to esomeprazole. The severity of TEAEs will be classified according to the study protocol as mild, moderate or severe.

Incidence of subjects who experienced TEAEs (frequency and the percentage of subjects) will be presented for each treatment and overall by:

- Overall summary of TEAEs;
- TEAEs by SOC
- TEAEs by SOC and PT;
- TEAEs by SOC, PT, and severity;
- TEAEs by SOC, PT, and relationship to the study drug;

All AEs will be listed. AE's that are serious, leading to death, leading to study discontinuation, or Treatment Emergent will be flagged.

For the purpose of inclusion in TEAE tables, the CRF question "Onset Date and Time" on "Adverse Events" page will be compared to the date and time of study drug administration, if the answer is not available, the imputed AE onset date will be used. Incomplete AE onset and end dates will be imputed similar to those rules as presented in [Section 8.9](#). Additional rules are as follows:

This document is confidential.

If an AE is recorded with an onset date corresponding to a study drug administration day, but the time is missing, then the AE will be assigned to the treatment as a TEAE.

If an AE is recorded with an onset date that does not correspond to the study drug administration day, but the time is missing, then the AE will be assigned to the treatment as a TEAE if AE onset date is after study drug administration date.

If an AE is recorded with an onset date where day and time are both missing, then the AE allocation to the treatment will be done on a case by case basis considering available information (e.g., AE end date, AE comments, subject disposition).

10.2 Clinical Laboratory Parameters

Laboratory analyses of blood and urine samples will be performed by the local laboratory.

The following clinical laboratory assessments will be performed:

Chemistry:	Standard serum chemistry will be collected. These include: Albumin, ALP, ALT, AST, Calcium, Chloride, Creatine kinase, Creatinine, GGT, Glucose, Phosphorus, Potassium, Sodium, Total bilirubin, Total protein, Urea (BUN)
Hematology:	Standard blood Hematology will be collected. These include: Hematocrit, Hemoglobin, Platelet count, RBC count, WBC count and differential (Basophils, Eosinophils, Lymphocytes, Monocytes, and Neutrophils)
Urinalysis:	Standard Urinalysis will be collected. This includes: Bilirubin, Blood (occult), Color and appearance, Glucose, Ketones, Leukocyte esterase, Nitrite, pH, Protein, Specific gravity, and Urobilinogen
Local Urinalysis (Microscopic)	Urine samples for Microscopic inspection will be performed only in the event of abnormal findings. This will include: Leukocytes, Erythrocytes, Epithelial cells, and the results, interpretation, and clinical significance of (Bacteria, Mucus, or other)

Clinical laboratory testing (hematology, chemistry, and urinalysis) will be performed at screening and at the End of Study visit.

Clinical laboratory values will be flagged as either high or low based on the reference ranges provided by the local laboratories for each laboratory parameter.

Individual clinical laboratory results and reference ranges will be presented in data listings.

10.3 Vital Sign Measurements

Vital signs measurements will include systolic and diastolic blood pressures (BPs), pulse rate (PR), respiratory rate (RR), and oral body temperature (BT).

Vital sign measurements will be performed at screening, BT on Day -1 of each period, Day 1

This document is confidential.

(within 1 hour before drug administration) of each treatment period, BT on Day 2 of each treatment period (Note: oral body temperature performed on Day 2 of Period 2 can be used as the oral body temperature required at End of Study), and at the end of Study Visit.

Vital signs will be summarized by time-point (Overall). Summary statistics will include mean, SD, minimum, median, and maximum. No inferential statistics will be presented. Data will be listed with abnormal values flagged.

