**Table 1-1 Schedule of Activities**

Procedure/Assessment	Screening	Treatment Periods 1 and 2 a			End of study visit *
		-1	1	2	
Study day	-28 to -2	-1	1	2	2
Confinement		x	x		
Discharge				x	
Informed consent	x				
Demography	x				
Medical history	x				
Physical examination b	x	x			x
Height, weight, BMI	x				
Vital signs (BP, PR, RR, BT)	x	x c	x c	x c	x
12-lead ECG	x				
Laboratory tests	x				x
COVID-19 test d	x	x		x	x
Virology	x				
Urine pregnancy test e	x				x
Serum pregnancy test e		x			
FSH f	x				
Urine drug screen	x	x			
Urine cotinine test	x	x			

Property of GSK Consumer Healthcare - Confidential

May not be used, divulged, published or otherwise disclosed without the consent of GSKCH  
SOP-208661 Clinical Protocol Template v7.0

Procedure/Assessment	Screening	Treatment Periods 1 and 2 a			End of study visit *
		-1	1	2	
Study day	-28 to -2	-1	1	2	2
Alcohol breath test	x	x			
Inclusion/exclusion assessment	x		X g		
Randomization h			x		
Drug administration			x		
PK blood sampling i			x	x	
Concomitant treatments	x	x	x	x	x
Adverse events j	x	x	x	x	x

Abbreviations: BMI, BP, PR, RR, BT, ECG, FSH, PK

Footnotes:

\*These assessments are also to be conducted for subjects who discontinue study drug. End of Study visit will occur before discharge, on study Day 2 of Period 2.

aThe washout period between each drug administration will be at least 7 days.

bA full physical examination will be performed at screening and a brief physical examination will be performed on Day -1 in each treatment period and end of study.

cBlood pressure (BP), pulse rate (PR), respiratory rate (RR), oral body temperature (BT): pre-treatment on Day 1 (within 1 hour before drug administration) of each treatment period. Oral body temperature (BT) on Day -1 and Day 2 of each treatment period (Note: oral body temperature performed on Day 2 of Period 2 can be used as the oral body temperature required at End of Study).

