### 12.3.3 Safety Analysis(es)

The assessment of safety will be based on the frequency and severity of treatment emergent AEs (TEAEs) i.e., AEs that are emergent or that worsen after the first study product (test or reference) administration.

The incidence of TEAEs will be summarized by presenting, for each treatment, the number and percentage of subjects having any AE, any AE in each MedDRA System Organ Class (SOC) and having each individual AE. The subset of AEs suspected of a relationship to study drug will be presented in a similar manner. All TEAEs will be also tabulated by severity. Any other information collected (e.g., action taken, duration, outcome) will be listed. AEs will be assigned to the treatment administered immediately prior to the onset. Adverse events due to COVID-19, if any, will be listed and tabulated separately.

Vital signs including temperature will be summarized by time-point and treatment. Summary statistics will include mean, standard deviation, minimum, median, and maximum. No inferential statistics will be presented. Data will be listed with abnormal values flagged.

Medical history and physical examination, as applicable, will be listed with abnormal values flagged.

Laboratory data and ECGs collected at screening and used for inclusion/exclusion criteria will be considered source data, and will not be required to be reported, unless otherwise noted.

Property of GSK Consumer Healthcare - Confidential

May not be used, divulged, published or otherwise disclosed without the consent of GSKCH  
SOP-208661 Clinical Protocol Template v7.0

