AUC	area under the curve
AUC_{0-t}	area under the concentration-time curve from time 0 to the time of the last measurable sampling time point, t
AUC_{0-inf}	area under the concentration time curve from time 0 to infinity
AZ	AstraZeneca
BDR	blinded data review
BLOQ	below the lower limit of quantification
BMI	body mass index
BP	blood pressure
BUN	blood urea nitrogen
CG	Catalent Guayama
CI	confidence interval
C_{max}	peak or maximum observed concentration
CRF	case report form
CSR	clinical study report
EC	ethics committee
ECG	electrocardiogram
eCRF	Electronic Case Report Form
FSH	follicle stimulating hormone
GCP	Good Clinical Practice
GGT	gamma glutamyl transpeptidase
HIV	human immunodeficiency virus

This document is confidential.

Version: Draft 1.0 11-Mar-2022

Controlled Document ID: CCI, Effective Date 29-Jul-2019

Filing requirements: TMF

Abbreviation	Description
ICF	informed consent form
ICH	International Conference on Harmonization
IEC	Independent Ethics Committee
IRB	institutional review board
MCH	Mean corpuscular hemoglobin
MCHC	Mean corpuscular hemoglobin concentration
MCV	Mean corpuscular volume
MedDRA	medical Dictionary for Regulatory Activities
N/A	not applicable
PCR	polymerase chain reaction
PK	pharmacokinetics
PR	pulse rate
PT	preferred term
QC	quality control
RBC	red blood cell
SAE	serious adverse event
SAP	statistical analysis plan
SD	Standard deviation
SOC	system organ class
SOP	standard operating procedure
$t_{1/2}$	terminal half-life
TLFs	tables, listings and figures
THC	tetrahydrocannabinol
t_{max}	time to reach maximum concentration
WBC	white blood cell

This document is confidential.

Version: Draft 1.0 11-Mar-2022

Controlled Document ID: CCI, Effective Date 29-Jul-2019

Filing requirements: TMF

2. Purpose

The purpose of this statistical analysis plan (SAP) is to ensure that the data listings, summary tables, and figures which will be produced, and the statistical methodologies that will be used, are complete and appropriate to allow valid conclusion regarding the study objectives. Safety and pharmacokinetic (PK) analyses will all be described.

This SAP is based on the following documents:

- Protocol No. 218246, Version 1.0 dated 25-Nov-2021 (PPD CCI) Project No. CCI
- Electronic Case Report Form (eCRF) Draft 1.0, dated 10-Feb-2022

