3.2.2 Safety objective

- Assess the safety profile (local and systemic) of both products

4. Endpoints

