7.3 Key Definitions

Study Day:

Study day will be calculated using first study drug administration (either Test or Reference) date as the reference date. If the date of interest occurs on or after the first study drug administration date, study day will be calculated as (date of interest – first study drug administration date) + 1. If the date of interest occurs prior to the first study drug administration date, study day will be calculated as (date of interest – first study drug administration date). There will be no study day 0.

Prior medication:

Medication/treatments taken within 90 days of signing the informed consent form will be documented as a prior medication/treatment.

Concomitant medication:

Medications/treatments taken after the first study drug administration will be documented as concomitant medication/treatments.

Treatment: Treatment is assigned as the last received treatment, except in the case of pre-dose measurements. Any non-adverse event assessment occurring on the same calendar date as a given treatment before dosing would be attributed to the same treatment given on that calendar day. If no treatment was applied on the same calendar day then any measurements pre-dose will not be summarized by treatment. Adverse events will be summarized only by the last received treatment.

Height:

Height (in cm) = height (in inches) * 2.54

Weight:

Weight (in kg) = weight (in lbs) * 0.4536

BMI:

BMI (kg/m²) = Weight(kg)/[Height(m)²]

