10.4 Physical Examination

A full physical examination will be performed at screening. A brief physical examination will be performed on Day -1 of each period and the End of Study visit.

A full physical examination will include head, ears, eyes, nose, mouth, skin, heart and lung examinations, lymph nodes, gastrointestinal, musculoskeletal, vascular and neurological systems. A brief physical examination will be focused on general appearance, heart (Cardiovascular), and lung (Respiratory) findings, as well as towards subject reported symptoms.

Any untoward findings identified on physical exams conducted after the administration of the first study drug administration will be captured as an adverse event, if those findings meet the definition of an adverse event.

11. Changes from the Protocol

The following text from the protocol was included by error and was not considered for this SAP as baseline corrections for plasma concentrations is not planned:

“Missing values of λ_z can be estimated from the subject’s λ_z value from the other treatment. If a λ_z value cannot be calculated from the other treatment, then the λ_z will be obtained from the treatment mean value for subjects with non-missing values of λ_z in the period in which it is not available. This estimated λ_z can be used to calculate other λ_z dependent variables. This λ_z value derivation is only applied for pre-dose concentration adjustments.”

This document is confidential.

12. Reference List

None

-

This document is confidential.

Version: Draft 1.0 11-Mar-2022

Controlled Document ID: CCI, Effective Date 29-Jul-2019

Filing requirements: TMF

13. Quality Control

SAS programs are developed to produce outputs such as analysis data sets, summary tables, data listings, figures or statistical analyses. These will be developed and undergo quality control as per SOPs CCI and CCI

This document is confidential.

Version: Draft 1.0 11-Mar-2022

Controlled Document ID: CCI, Effective Date 29-Jul-2019

Filing requirements: TMF

14. Appendices

None

This document is confidential.

Version: Draft 1.0 11-Mar-2022

Controlled Document ID: CCI, Effective Date 29-Jul-2019

Filing requirements: TMF

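### SAP 10.3 summarizes vital signs overall where protocol 12.3.3 requires a split by treatment, and SAP section 11 does not declare the change

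*SAP*

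**What the plan says.** Protocol 12.3.3 sets the rule: "Vital signs including temperature will be summarized by time-point and treatment". It then names the descriptive statistics, rules out inferential statistics and asks for listings with abnormal values flagged.

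SAP 10.3 keeps all of that but opens differently: "Vital signs will be summarized by time-point (Overall"). The treatment split has gone.

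The safety objective in SAP 3.2.2 is "Assess the safety profile (local and systemic) of both products", and SAP 4.2 names vital signs among the safety endpoints. SAP 7.3 has a rule for attributing assessments to a product: "Treatment is assigned as the last received treatment, except in the case of pre-dose measurements". Under that rule, a pre-dose value taken on a dosing day goes to the product given that day. A pre-dose value taken on a day without dosing is left out of by-treatment summaries.

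SAP section 11 lists one departure from the protocol, the imputation of missing terminal rate constants. Vital signs do not appear there.

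**The concern.** The objective concerns the safety profile of both products, and the protocol promises a vital-signs summary for each. In a two-sequence crossover, both products are given in each period, so any post-dose row without a treatment split mixes subjects who took Test with subjects who took Reference. Such a row cannot show what was seen after either one.

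The SAP also has a section for departures and uses it for another item. A reader of the study report would therefore find a named safety endpoint summarized differently from the protocol, with no explanation.

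**Working it through.** The plan states no figure to reproduce on this point. The check compares the texts, then counts what a treatment split could show.

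**1. Is the difference real and unexplained?**
- Protocol 12.3.3: by time-point and treatment. SAP 10.3: by time-point, overall. Neither sentence is redacted.
- The SAP is based on "Protocol No. 218246, Version 1.0 dated 25-Nov-2021", while the current protocol incorporates Amendment 1. The amendment's change list does not mention 12.3.3, so the version gap does not account for the difference.
- SAP section 11 is silent on it.

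**2. Which scheduled rows carry post-dose information?** Inputs are protocol Table 1-1, protocol 8.2.8 and SAP 10.3. The four Day 1 measurements are "pre-treatment on Day 1 (within 1 hour before drug administration) of each treatment period". Temperature is also scheduled separately: "Oral body temperature (BT) on Day -1 and Day 2 of each treatment period".

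| Time-point | Measured | Relation to dosing | Attribution under SAP 7.3 |
|---|---|---|---|
| Screening | BP, PR, RR, temperature | before any product | none |
| Period 1 Day -1 | temperature | before any product | none |
| Period 1 Day 1 | BP, PR, RR, temperature | pre-dose | Period 1 product |
| Period 1 Day 2 | temperature | about 24 h after dose 1 | Period 1 product |
| Period 2 Day -1 | temperature | washout, before dose 2 | none |
| Period 2 Day 1 | BP, PR, RR, temperature | pre-dose | Period 2 product |
| Period 2 Day 2 / End of Study | BP, PR, RR, temperature | about 24 h after dose 2 | Period 2 product |

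Period 2 Day 2 temperature is counted once, because the plan lets it serve as the End of Study value.
- BP, PR, RR: 1 + 1 + 1 + 1 = 4 time-points, of which 1 is post-dose.
- Temperature: 7 time-points, of which 2 are post-dose.

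**3. What comparison would the split allow?** Each completer has a Day 2 temperature after each product, so temperature can be set side by side within subjects. BP, PR and RR are read post-dose only after Period 2, so a completer contributes to one product only. A split there compares different subjects.

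**4. How many subjects per product in a period's row?** Assume balanced sequences; SAP 5.3.1 specifies block randomization but no ratio. Of 49 randomized, 49 / 2 = 24.5, so 24 or 25 per product. Of 41 evaluable, 41 / 2 = 20.5, so 20 or 21. The overall row merges these two groups.

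**5. Can the split be produced from planned data?** Yes. SAP 7.3 assigns a product to every Day 1, Day 2 and End of Study value, and no further measurement is needed.

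**The case against.** The strongest reply is that little is lost. Safety by product rests mainly on treatment-emergent adverse events, which SAP 10.1 presents for each treatment and overall. Protocol 10.1 counts an abnormal vital sign judged clinically significant as an adverse event, so one arising after dosing would enter those by-treatment tables. Individual values are listed with abnormal ones flagged, the table is purely descriptive, and few of its rows are post-dose. All of this stands and limits the severity. It does not remove the mismatch: sparse data could justify pooling, but the SAP does not say so, and a listing does not replace a summary the protocol specifies.

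Three stronger readings are tempting and are not supported:

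- A reader might infer that the SAP contradicts itself because the overall table does not use the 7.3 rule. That rule says how to attribute a value when results are shown by treatment; it does not require any table to be split. The departure is from the protocol only.
- A reader might infer that pooling materially dilutes a product difference, since at an even mix a mean shift on one product appears at half its size. That is generic arithmetic. It bears only on the post-dose rows, and nothing in the documents suggests a shift to expect. Screening and Day 1 pre-dose rows contain no effect of a product not yet given.
- A reader might infer that every vital-sign row should be split. SAP 7.3 keeps screening and Day -1 values out of by-treatment summaries, so those rows have to stay overall.

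The table shells are in a separate document not available here, so the final layout cannot be confirmed. That does not excuse the SAP wording.

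**Conclusion.** The departure is real and undeclared, and SAP 10.3 is wrong as written. Its severity is minor. The loss is confined to one descriptive table. The informative rows are Day 2 temperature in each period and End of Study BP, PR and RR; the latter would support only a between-subject comparison.

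A reader might conclude that the study cannot describe the safety of each product. The documents do not support that, given the by-treatment adverse-event tables and the flagged listings. The bioequivalence analysis and the sample size are unaffected.

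The conclusion rests on the wording of protocol 12.3.3 and SAP 10.3 and 11, and on the scheduled time-points. The row counts per product also assume balanced sequences.

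**What to change.** In SAP 10.3, replace the overall summary with the following:

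- Day 1 pre-dose, Day 2 and End of Study values: summarize by time-point and treatment under SAP 7.3. Day 1 goes to that day's product and is labelled as that treatment's baseline. Day 2 and End of Study go to the last product received.
- Screening and Day -1 values: keep as overall rows.
- An overall column elsewhere is optional.

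If pooling is intended, leave 10.3 as it is, but declare the departure in SAP section 11 and justify it. Either way, align the table shell.

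The cost is a short edit to SAP 10.3 and one class variable in the table program, with no new data. The SAP text supplied is marked Draft 1.0, so the edit can go in before it is finalized.
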